DCR	disease control rate
DLT	dose-limiting toxicity
DLRT	dose level review team
DOR	duration of response
DoSD	duration of stable disease
DRT	data review team
ECG	electrocardiogram
ECOG	Eastern Cooperative Oncology Group
GSO	Global Study Operation
IPD	important protocol deviation
KM	Kaplan Meier
KRAS	Kirsten rat sarcoma
LTFU	long term follow-up
MedDRA	medical dictionary for regulatory activities
MRI	magnetic resonance imaging
NE	not evaluable
OR	objective response
PD	progressive disease
PFS	progression-free survival
PK	pharmacokinetics
РО	administered orally
PR	partial response
QD	once daily
1	

Protocol Number: 20190147

Date: 17FEB2022 Page 6 of 28

Abbreviation	Explanation
QTc	corrected QT interval
QTcF	Fridericia-corrected QT interval
RECIST	Response Evaluation Criteria in Solid Tumors
SAE	serious adverse event
SAP	statistical analysis plan
SFU	safety follow-up
TEAE	Treatment emergent adverse event
t _{max}	time to achieve C _{max}
TTR	time to response
WHO	World Health Organization

Protocol Number: 20190147

Date: 17FEB2022 Page 7 of 28

1. Introduction

The purpose of this Statistical Analysis Plan (SAP) is to provide details of the statistical analyses that have been outlined within the protocol amendment 4 for study 20190147 AMG 510 dated 05 January 2022. The scope of this plan includes the interim analysis, the primary analysis and final analyses that are planned and will be executed by the Amgen Global Biostatistical Science department unless otherwise specified.

2. Objectives, Endpoints and Hypotheses

2.1 Objectives and Endpoints

Objectives	Endpoints		
Primary			
To evaluate the safety and tolerability of AMG 510 in adult subjects of Chinese descent with KRAS p.G12C-mutant advanced/metastatic solid tumors	Subject incidence of dose-limiting toxicity (DLT), treatment-emergent adverse events, treatment-related adverse events, and changes in vital signs, electrocardiograms (ECGs), and clinical laboratory tests		
To characterize the pharmacokinetics (PK) of AMG 510 in subjects of Chinese descent when administered orally (PO)	PK parameters of AMG 510 including, but not limited to, maximum observed plasma concentration (C _{max}), time to achieve C _{max} (t _{max}), and area under the plasma concentration time curve (AUC)		
Secondary			
To evaluate the preliminary efficacy of AMG 510 as a mono-therapy in subsets of solid tumors with the KRAS p.G12C mutation	Objective response, duration of response, progression-free survival (PFS), disease control, time to response (TTR), and duration of stable disease measured by computed tomography (CT) or magnetic resonance imaging (MRI) and assessed per Response Evaluation Criteria in Solid Tumors (RECIST) version 1.1 guidelines		

2.2 Hypotheses and/or Estimations

No statistical hypothesis will be tested.

Protocol Number: 20190147

Date: 17FEB2022 Page 8 of 28

3. Study Overview

3.1 Study Design

This is a non-randomized, open-label, multi-center phase 1 study to evaluate safety, tolerability, PK, and preliminary efficacy of AMG 510 PO QD in subjects of Chinese descent with KRAS p.G12C-mutant advance/metastatic solid tumors. This study will be conducted at sites in Hong Kong and Taiwan.

Up to 18 subjects will be enrolled into the study. Enrollment into the first dose level cohort (cohort 1) may be from any eligible $KRAS\ p.G12C$ -mutant advanced/metastatic solid tumor type. Six initial subjects will be enrolled into cohort 1 and will receive 960 mg of AMG PO QD. If ≤ 1 dose-limiting toxicity (DLT) is observed in the first 6 subjects, up to 6 additional subjects may be enrolled into cohort 1 to collect additional PK, safety, and preliminary efficacy at the 960 mg dose. If ≥ 2 DLT are observed in the first 6 subjects in cohort 1, an additional 6 subjects will be enrolled into a second dose level cohort (cohort 2), wherein the dose will be reduced to 720 mg AMG 510 PO QD. If ≤ 1 DLT is observed in the first 6 subjects in cohort 2, up to 6 additional subjects may be enrolled in cohort 2 to gather additional PK, safety and preliminary efficacy at the 720 mg dose.

The safety and tolerability data from the first 6 subjects at the 960 mg dose level will be reviewed by a Dose Level Review Team (DLRT) 21 days after receiving the first dose AMG 510. The DLRT will recommend whether cohort 1 should be continued at 960 mg or be modified and whether an additional 6 subjects could be enrolled in cohort 1 or if the 720 mg dose cohort (cohort 2) should be opened. If the DLRT makes the recommendation to enroll the next 6 subjects at the 720 mg AMG 510 dose in cohort 2, the DLRT will again review safety and tolerability data when the sixth enrolled subject at the 720 mg dose has the opportunity to receive AMG 510 for 21 days. The DLRT will recommend whether cohort 2 should be continued at 720 mg or be modified and whether an additional 6 subjects could be enrolled in cohort 2. The dose modification strategy is described in Protocol Section 6.2. Administration of AMG 510 may continue until there is evidence of disease progression, intolerance to study medication, or withdrawal of consent.

Subjects will have a safety follow-up (SFU) visit approximately 30 (+7) days after the last dose of AMG 510 or before any new anticancer treatment is started, whichever occurs first. The SFU visit will be the end of visit for each subject.

Protocol Number: 20190147

Date: 17FEB2022 Page 9 of 28

3.2 Sample Size

Up to 18 subjects will be enrolled in this study. Six DLT-evaluable subjects will be enrolled in cohort 1. If the 960 mg dose (cohort 1) is recommended to be safe and tolerable by the DLRT, up to 6 additional subjects may be enrolled in cohort 1 to gather additional safety, PK, and preliminary efficacy data (up to 12 subjects total enrolled in the study) at the 960 mg dose. Alternatively, if the DLRT recommends to open cohort 2 (720 mg dose), 6 DLT-evaluable subjects will be enrolled in cohort 2. If the DLRT then make the recommendation to continue cohort 2 at 720 mg, up to 6 additional subjects (up to 18 subjects total enrolled in the study) may be enrolled in cohort 2 to gather additional PK, safety, and preliminary efficacy at the 720 mg dose.

The sample size of 6-DLT evaluable subjects in the dose exploration phase for DLRM is based on practical considerations and is consistent with conventional oncology studies. With 6 DLT evaluable subjects, there is a 47% to 91% probability of observing at least 1 DLT if the true DLT rate is 10% to 33%.

3.3 Adaptive Design

De-escalation to a lower dose will be decided in the Dose Level Review Team.

4. Covariates and Subgroups

4.1 Planned Covariates

There are no planned covariates for this study.

4.2 Subgroups

Subgroup analyses for selected secondary endpoints (ORR and PFS) may be performed by cancer type (NSCLC, Colon cancer and Pancreatic cancer).

5. Definitions

AUC:

The area under the plasma drug concentration-time curve (AUC) reflects the actual body exposure to drug after administration of a dose of the drug.

Baseline:

For any variable, unless otherwise specified the baseline is the last non-missing assessment taken prior to the first administration of AMG 510 treatment. Where baseline measurements are taken on the same day as AMG 510 and no times are present, it will be assumed that these measurements are taken prior to the study specified treatment being administered.

Protocol Number: 20190147

Date: 17FEB2022 Page 10 of 28

Baseline ECG Values in Triplicate:

The mean of the three triplicate ECG results should be calculated for baseline. If fewer than three triplicate ECG results are available, the mean of available triplicate should be calculated. For all post-baseline ECG, the mean of one triplicate ECG results at the same assessment will be calculated and used in the analysis. When an ECG is missing within a triplicate, all available data will be averaged for that time point.

Best Overall Response (BOR):

The best overall response for a subject is the best observed disease response per RECIST v1.1.

BOR is defined as the best response in the following order: CR, PR, SD, PD, or NE, where CR and PR require confirmation by a repeat, consecutive scan at least 4 weeks after the first documentation of response. A BOR of SD requires an on-study imaging of SD or better no earlier than 5 weeks after cycle 1 day 1, otherwise the BOR will be not evaluable (NE). Please see the details in Protocol Appendix 8 and refer Appendix A for deriving BOR calculation algorithm.

Change from Baseline:

Change from Baseline is the arithmetic difference between post-dose assessment and Baseline value.

Change (absolute) from Baseline = (Post-baseline Value - Baseline Value)

Percent Change from Baseline = [(Post-baseline Value-Baseline Value) / Baseline Value] ×100

Diseases Control Rate (DCR):

Diseases Control Rate is defined as the proportion of subjects in whom the best overall response is determined as CR, PR, or SD.

DLT:

A DLT is defined as any adverse event meeting the criteria listed in Protocol Section 6.2.2 occurring during the first treatment cycle of AMG 510 (day 1 through day 21) where a relationship to AMG 510 cannot be ruled out.

Duration of Response (DOR):

Protocol Number: 20190147

Date: 17FEB2022 Page 11 of 28

The duration of response is defined as time from first evidence of confirmed PR or CR to disease progression or death due to any cause, whichever occurs first. DOR will be calculated only for subjects who achieve a confirmed BOR of PR or CR.

DOR (months)= (PD or death date – response start date +1) x 12 / 365.25

Subjects will be censored following the censoring strategy described in Table 5-1.

Duration of Stable Disease (DoSD):

Duration of stable disease will be measured from the start of treatment to disease progression or death, whichever occurs first. DoSD will be calculated in subjects with best overall response SD. Subjects will be censored following the censoring strategy described in Table 5-1.

End of IP Administration (End of IP Admin):

End of IP Admin for each subject is defined as the date the decision was made to end IP as recorded on the End of Investigational Product Administration CRF page.

End of Study (Individual Subject):

End of study for each subject is defined as the date the subject last completed a protocol-specified procedure. The date will be recorded on the End of Study CRF page.

End of Study (End of Trial):

The end of study date is defined as the date when the last subject across all sites is assessed or receives an intervention for evaluation in the study (ie, last subject last visit), following any additional parts in the study (eg, safety follow-up), as applicable.

Investigational Product:

The term 'investigational product' is used in reference to AMG 510.

Last Investigational Product Dose Date:

The last IP date for each subject is defined as the latest date IP administered.

Objective Response Rate (ORR):

Objective response rate is defined as the proportion of subjects with a BOR of confirmed CR or PR.

Progression Fee-Survival (PFS):

Protocol Number: 20190147

Date: 17FEB2022 Page 12 of 28

The PFS is defined as interval from the first dose of AMG 510 until disease progression or death due to any cause, whichever comes first in the absence of subsequent anticancer therapy. The censoring rules for the progression-free survival analysis are detailed in Table 5-1.

PFS (months) = (PD or death date – start of treatment date +1) x12/365.25

Table 5-1. Date of Progression or Censoring for PFS

Situation (before data cutoff/ end of	Main Analysis			
study)	Date of Event or Censor	Outcome		
Documented PD or death, no prior new anticancer therapy	Earlier of PD or death date	Event		
No evaluable post-baseline tumor assessments, no death	Date of first dose	Censor		
No documented PD, no death, but new anti- cancer therapy recorded.	Date of last evaluable assessment before start of new anti-cancer therapy	Censor		
New anti-cancer therapy started before documented of PD or death	Date of last evaluable assessment before start of new anti-cancer therapy	Censor		
No documented PD or death, no new anti- cancer therapy	Date of last evaluable assessment	Censor		
Death or PD immediately after more than 1 consecutively missed tumor assessment	Date of last evaluable assessment prior to missing assessments	Censor		

Relative Dose Intensity:

Relative dose intensity is calculated as actual dose intensity/planned dose intensity where

- Cumulative actual dose (mg) is defined as the total dose given during the study treatment exposure. For subjects who did not take any drug the cumulative actual dose by definition is 0 mg
- Actual dose intensity for subjects with non-zero duration of exposure is defined
 as: cumulative actual dose (mg)/duration of exposure (days), where duration of
 exposure = date of last non-missing dose date of first dose +1. For subjects
 who did not take any drug the actual dose intensity is 0 mg/day.
- Cumulative planned dose is the per-protocol planned dose accumulated over the planned duration on the study treatment.

Protocol Number: 20190147

Date: 17FEB2022 Page 13 of 28

 Planned dose intensity for subjects with non-zero duration of exposure is defined as: cumulative planned dose (mg)/planned duration of exposure (days), where planned duration of exposure = date of last dose – date of first dose +1.

Safety Follow-Up:

The safety follow-up visit should occur approximately 30 (+7) days after last dose of AMG 510 or before any new anticancer treatment is started, whichever occurs first.

Study Day 1:

It is defined as the first day of the treatment being administrated to the subject.

Study Day:

Post-study day: study day = (date - date of Study Day 1) +1

Pre-study day: study day = (date - date of Study Day 1)

Time to Response (TTR):

Time to response is defined as time from the start of treatment until the first evidence of PR or CR. TTR will be calculated only for subjects who achieve a best overall response of confirmed PR or CR.

Treatment-Emergent Adverse Event (TEAE):

Events categorized as Adverse Events (AEs) starting on or after first dose of investigational product as determined by "Did event start before first dose of investigational product" equal to "No" or missing on the Events CRF and up to the End of Study date.

Treatment-Related Adverse Event (AE):

A treatment-related AE is any treatment-emergent AE with the relationship flag on the Events eCRF indicating there is a reasonable possibility that the event may have been caused by investigational medicinal product. In the unlikely event that the relationship is missing, the treatment-emergent event will be considered treatment-related and documented in a footnote of the treatment-related summary.

6. Analysis Sets

The analysis of all endpoints, unless noted otherwise, will be conducted on the Safety Analysis Set.

Protocol Number: 20190147

Date: 17FEB2022 Page 14 of 28

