8.2.4 Adverse Events and Serious Adverse Events

8.2.4.1 Time Period and Frequency for Collecting and Reporting Safety Event Information

8.2.4.1.1 Adverse Events

The adverse event grading scale to be used for this study will be the CTCAE version 5.0 and is described in Section 11.4.

The investigator is responsible for ensuring that all adverse events observed by the investigator or reported by the subject that occur after the first dose of investigational product/study treatment through the SFU (end of study) visit are reported using the Events eCRF. All other adverse events possibly related to any study procedures will be reported from the signing of the ICF through the SFU (end of study) visit using the Events eCRF.

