8.2.4.1.2 Serious Adverse Events

The investigator is responsible for ensuring that all serious adverse events observed by the investigator or reported by the subject that occur after signing of the ICF through **the safety follow-up visit** or 30 days after the last day of dosing interval of investigational product(s)/protocol-required therapies, whichever occurs later, are reported using the Events CRF.

All serious adverse events will be collected, recorded and reported to the sponsor or designee within 24 hours of the investigator's awareness of the event, as indicated in Section 11.4. The investigator will submit any updated serious adverse event data to the sponsor within 24 hours of it being available.

The criteria for grade 4 in the CTCAE version 5.0 grading scale differs from the regulatory criteria for serious adverse events. It is left to the investigator's judgment to report these grade 4 abnormalities as serious adverse events.

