
Study and Site Closure

Amgen or its designee may stop the study or study site participation in the study for medical, safety, regulatory, administrative, or other reasons consistent with applicable laws, regulations, and GCP.

Both Amgen and the investigator reserve the right to terminate the investigator's participation in the study according to the Clinical Trial Agreement. The investigator is to notify the IRB/IEC in writing of the study's completion or early termination and send a copy of the notification to Amgen.

Subjects may be eligible for continued treatment with Amgen investigational product(s) by an extension protocol or as provided for by the local country's regulatory mechanism. However, Amgen reserves the unilateral right, at its sole discretion, to determine whether to supply Amgen investigational product(s) and by what mechanism, after termination of the study and before the product(s) is/are available commercially.

Compensation

Any arrangements for compensation to subjects for injury or illness that arises in the study are described in the Compensation for Injury section of the Informed Consent that is available as a separate document.

11.4 Appendix 4. Safety Events: Definitions and Procedures for Recording, Evaluating, Follow-up and Reporting

Definition of Adverse Event

Adverse Event Definition

- An adverse event is any untoward medical occurrence in a clinical study subject irrespective of a causal relationship with the study treatment.
- Note: An adverse event can therefore be any unfavorable and unintended sign (including an abnormal laboratory finding), symptom, or disease (new or exacerbated) temporally associated with the use of a treatment, combination product, medical device or procedure.
- Note: Treatment-emergent adverse events will be defined in the statistical analysis plan.

Events Meeting the Adverse Event Definition

- Any abnormal laboratory test results (hematology, clinical chemistry, or urinalysis) or other safety assessments (eg, electrocardiogram, radiological scans, vital signs measurements), including those that worsen from baseline, that are considered clinically significant in the medical and scientific judgment of the investigator (ie, not related to progression of underlying disease).
- Exacerbation of a chronic or intermittent pre-existing condition including either an increase in frequency and/or intensity of the condition.

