 - adverse event diagnosis or syndrome(s), if known (if not known, signs or symptoms);
 - dates of onset and resolution (if resolved);
 - Did the event start prior to first dose of investigational product;
 - assessment of seriousness;
 - severity (or toxicity defined below);
 - assessment of relatedness to investigational product (AMG 510), other protocolrequired therapies, and/or study-mandated **activity and/or** procedures and;
 - action taken and
 - outcome of event.
- If the severity of an adverse event changes from the date of onset to the date of resolution, record as a single event with the highest grade on the Events electronic CRF.
- It is not acceptable for the investigator to send photocopies of the subject's medical records to the sponsor in lieu of completion of the Events CRF page.
- If specifically requested, the investigator may need to provide additional follow-up information, such as discharge summaries, medical records, or extracts from the medical records. In this case, all subject identifiers, with the exception of the subject number, will be blinded on the copies of the medical records before submission to Amgen.
- The investigator will attempt to establish a diagnosis of the event based on signs, symptoms, and/or other clinical information. In such cases, the diagnosis (not the individual signs/symptoms) will be documented as the adverse event/serious adverse event.

Evaluating Adverse Events and Serious Adverse Events

Assessment of Severity

The investigator will make an assessment of severity for each adverse event and serious adverse event reported during the study. The assessment of severity will be based on:

The Common Terminology Criteria for Adverse Events, version 5.0 which is available at the following location: http://ctep.cancer.gov/protocolDevelopment/electronic_applications/ctc.htm.

Assessment of Causality

- The investigator is obligated to assess the relationship between investigational product, protocol-required therapies, and/or study-mandated **activity and/or** procedure and each occurrence of each adverse event/serious adverse event.
- Relatedness means that there are facts or reasons to support a relationship between investigational product and the event.
- The investigator will use clinical judgment to determine the relationship.

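### The treatment-emergent AE definition has no worsening clause, so read literally it leaves out an SAE or procedure-related AE already open at first dose that worsens on AMG 510

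*SAP*

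**What the plan says.** Protocol Section 11.4 leaves the definition of a treatment-emergent adverse event (TEAE) to the SAP. SAP Section 5 gives it as "Events categorized as Adverse Events (AEs) starting on or after first dose of investigational product as determined by" the Events CRF item on pre-dose start, which must be No or missing; the window closes at End of Study. Nothing is said about an event that was present earlier and became worse. The next definition builds on this one: "A treatment-related AE is any treatment-emergent AE with the relationship flag on the Events eCRF" showing a reasonable possibility of causation by the product.

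Protocol Section 11.4 lists the attributes that the investigator assigns to each event. One is "Did the event start prior to first dose of investigational product". It then says that if severity "changes from the date of onset to the date of resolution, record as a single event with the highest grade". Its follow-up rules send new or updated information to the Events CRF page first completed for the event.

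Two kinds of event reach the Events CRF before dosing. Protocol Section 8.2.4.1.2 covers "all serious adverse events observed by the investigator or reported by the subject that occur after signing of the ICF through" the safety follow-up period. Section 8.2.4.1.1 adds: "All other adverse events possibly related to any study procedures will be reported from the signing of the ICF through the SFU" visit.

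Section 11.4 also lists, among occurrences that are adverse events, "Exacerbation of a chronic or intermittent pre-existing condition including either an increase in frequency and/or intensity of the condition".

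**The concern.** TEAE definitions usually have two limbs: events that start on treatment, and events present beforehand that get worse on treatment. This SAP has only the first. That would do little harm if each on-treatment worsening produced a new record, but the protocol's rule for changing severity points the other way. An event opened in screening keeps its original start, its pre-dose flag and a single grade, the highest reached.

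Such an event is not a TEAE. Because treatment-related AEs are drawn from TEAEs, it is not treatment-related either, even if the investigator attributes the worsening to AMG 510. Both incidences are primary safety endpoints (Protocol Section 3), and the study's stated use is comparison with the global first-in-human Study 20170543 (Protocol Section 2.1). The omission can only lower the reported incidence.

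**Working it through.** The plan states no figure on this point. The check is a trace of the definitions, followed by simple arithmetic on size.

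**Trace by type of record**

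| Situation | Record under the protocol | Start flag | TEAE under SAP Section 5? |
|---|---|---|---|
| SAE or procedure-related AE open at first dose, worsens on AMG 510 | One record, original start, highest grade (11.4) | Yes | No, so not treatment-related either |
| Condition held as medical history, worsens on AMG 510 | New AE under the exacerbation clause (11.4) | No | Yes |
| Any event with the start flag missing | As recorded | Missing | Yes |
| Pre-dose event that resolves and recurs after dosing | New event with its own onset | No | Yes |

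Only the first row is a problem. It needs an event that is serious or procedure-related, is unresolved at first dose, and then increases in grade. Other conditions arising in screening belong to medical history, which Protocol Section 8.2.1.3 collects up to the start of treatment with the current grade of anything unresolved.

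**Can programming recover the first row later?** No. One record at its highest grade does not show whether the peak came before or after first dose. A worsening clause in the SAP could not be applied to such records without a change in what is recorded.

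**Effect of one missed subject on an incidence row:** 100/n percentage points.

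- n = 6: 100/6 = 16.7
- n = 12: 100/12 = 8.3
- n = 18: 100/18 = 5.6

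Summaries are planned by dose and a dose cohort has 6 to 12 subjects, so the first two apply within a dose; n = 18 applies only to a pooled table. The shift occurs only if the subject has no other event in the same row. It is therefore least likely for the any-TEAE row and more likely for a single preferred term or a treatment-related row.

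**How often?** The documents give no rate. Purely as an assumption, let q be the per-subject chance of a first-row event, between 2% and 10%. The chance of at least one such subject is 1 − (1 − q)^n.

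| n | q = 2% | q = 10% |
|---|---|---|
| 6 | 1 − 0.98^6 = 11.4% | 1 − 0.90^6 = 46.9% |
| 12 | 1 − 0.98^12 = 21.5% | 1 − 0.90^12 = 71.8% |
| 18 | 1 − 0.98^18 = 30.5% | 1 − 0.90^18 = 85.0% |

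The width of this range shows how little can be said about frequency. The true rate could also lie below 2%.

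**The case against.** The best defence is that few events can fall into the gap and that other outputs would show them.

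- **Few candidates.** A non-serious pneumonia in screening is medical history, and its worsening is a new AE. If it were serious, exclusion criterion 205 (recent infection needing IV antibiotics) or criterion 224 might keep the subject out. A screening biopsy is optional and arises only when KRAS status is not on record and archived tissue is unavailable. This stands, and it limits the point to SAEs and procedure-related AEs still open at first dose.
- **A site could open a new record.** The exacerbation clause makes greater intensity of a chronic or intermittent pre-existing condition an AE in its own right. This stands in part. A reader might infer that a pre-dose event that worsens can never be counted; the documents do not support that. They contain two rules, one pointing to a new record and one to a single record, and do not say which governs an event already on the Events CRF. Sites may therefore record the same situation differently.
- **Other outputs do not use the TEAE definition.** DLTs are defined by events in days 1 to 21 (Protocol Section 6.2.2). The dose level review considers AEs and DLTs in all subjects (Section 9.4.1.1.1). Laboratory shift tables use the worst on-study value (SAP Section 9.6.3). The serious and fatal AE tables in SAP Section 9.6.2 are not expressly restricted to TEAEs. This stands: a reader might infer that on-drug worsening vanishes from safety reporting altogether, and it does not. None of these outputs, however, restores the TEAE and treatment-related incidences.
- **Comparability.** If Study 20170543 uses a flag-only definition, changing it here alone could disturb the comparison. That study's definition is not in these documents. The risk is real but is met by reporting both counts.

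**Conclusion.** The definition should be corrected. On its literal text, an SAE or procedure-related AE open at first dose that worsens on AMG 510 is left out of two primary incidences, always in the direction of better tolerability. The stronger reading, that pre-existing conditions in general are lost, fails because worsening of a medical-history condition is a new AE and is counted.

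The size is 1/n per missed subject, subject to the condition on other events in the row. The number of such subjects is unknown and may be zero. Dose decisions do not rest on the TEAE definition. The case for change is that the rule is incomplete as written, errs one way and is cheap to repair; no large expected bias has been shown. The conclusion assumes that sites follow the single-record rule for events already on the Events CRF.

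**What to change.** **SAP Section 5.** Define a TEAE as an adverse event that starts on or after the first dose of AMG 510, or that was present before the first dose and increases in CTCAE grade on or after it. The treatment-related definition can then stay as it is.

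**Protocol Section 11.4 and the CRF completion guide.** State that when an event already on the Events CRF at first dose increases in grade afterwards, the worsening is entered as a new record, with onset at the date of worsening, the pre-dose start item answered No, and its own causality assessment. State that the single-record rule otherwise applies, so that it no longer conflicts with the exacerbation clause. The SAP sentence alone is not enough, because the existing record does not date the peak grade.

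**Comparison with Study 20170543.** If that study used the flag-only definition, show the flag-only count beside the revised one.

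**Cost.** One sentence in the SAP, a short addition to the protocol and CRF guide, possible queries on pre-dose records already entered, and a slightly higher reported AE incidence. The change should be made before database lock, the point by which Protocol Section 9.4 requires the SAP to be final.
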